2.2 Sample Size Determination

In the UK Phase 2 study of patients with Gorlin syndrome (Pelle-926-201), the mean number of nSEBs (erroneously stated in the protocol as mean number of new BCCs in the Section on Sample size determinations) at 6 months was █ in the Patidegib Topical Gel, 2%, group with an SD of █, and a mean of 1.4 in the Vehicle Gel group with a SD of 1.52. The effect size was 0.81. Because the current trial is longer, more conservative assumptions are made. It is assumed that at 6 months, the mean number of nSEBs in the Patidegib Topical Gel, 2%, group will be 0.6, with an SD of █, while at 6 months the mean and SD in the Vehicle Gel group will be the same as in the Phase 2 study at 6 months for an effect size of 0.63. At 12 months, it is assumed that the means and SDs will be twice those of 6 months. With these assumptions, █ subjects in the Patidegib Topical Gel, 2%, group and 63 in the Vehicle Gel group (for a total of █ subjects) will give >90% power for a 2-sided 0.05 level statistical significance. To account for a 16% drop-out rate, approximately 150 subjects will be randomized.

The primary endpoint of number of qualifying nSEBs per subject by Month 12 may be affected by follow-up time. Based on the UK Phase 2 study (Pelle-926-201), it is projected that the power calculated above will be substantially similar unless marked differences are seen between the treatment arms in follow-up time. Sample size was calculated based on a Wilcoxon-Mann-Whitney test which is conservative if the underlying distribution is Negative Binomial.

2.3 Study Populations

The enrolled population, defined as all subjects who signed informed consent, will be used for study disposition summaries. The primary population for efficacy analyses will be the Intent-to-Treat (ITT) population, defined as all subjects who were randomized. Subjects will be assigned to treatment groups as randomized. The per-protocol (PP) population will be used for supportive efficacy analyses and is defined as all randomized subjects who completed 12 months of treatment with between █ treatment compliance and without any major protocol deviations in regard to inclusion/exclusion criteria or prohibited concomitant medications. In the PP population, subjects will be assigned to treatment groups as treated (not as randomized). The Safety population will consist of all subjects who have applied treatment at least once and will be assigned to treatment groups as treated. Subjects who receive both Patidegib and Vehicle will be summarized in the Patidegib group.

Listings of all subjects who signed informed consent but did not fulfill all eligibility criteria, randomization assignments, and subject disposition will be created.

2.4 Subject Accounting and Baseline Characteristics

Subject disposition including population counts, treatment discontinuation reason, duration on study, completion of study (defined as being contacted for the 30 day follow-up), and reason for study discontinuation will be summarized for all subjects who signed an informed consent (enrolled population). A Kaplan-Meier plot of the time to treatment discontinuation will be presented in the Safety

Pelle-926-301 Statistical Analysis Plan

17 June 2020

Population. Demographic and baseline characteristics will be summarized for all subjects in the ITT Population. Demographics will be presented in a listing. A summary of baseline efficacy parameters including time since diagnosis of BCNS, number of SEBs at baseline, number of BCCs including and excluding SEBs, and history of prior HHI therapy use will be provided in the ITT Population. Medical history, prior and concomitant medications/products, prior and concomitant procedures/therapies, study completion status and reasons for discontinuation will also be summarized and listed for this population. Prior medications/products and procedures/therapies are those that started and ended prior to the date of initial dose of study drug and are not ongoing at baseline. Concomitant medications are defined as any medication ongoing at baseline (date of first dose) or which are taken at/after date of first study medication.

A summary and a listing of subjects with any blood relatives with BCNS will be provided. A table of Gorlin diagnostic criteria will be presented.

2.5 Efficacy Analyses

2.5.1 Primary Efficacy Analysis

The primary endpoint is the number of nSEBs per subject by Month 12. A nSEB is a histologically verified BCC that was surgically removed because of possible functional facial/health impairment as determined by the Investigator. Also, nSEBs are facial BCCs with a longest diameter of ≥ 5 mm that:

- a. were not SEBs at Baseline,
- b. have grown by █ mm in longest diameter from Baseline, and
- c. have been verified histologically.

If two or more lesions merge together and become a nSEB, then this will count as only 1 nSEB. If an investigator indicates that the lesion grew at least █ mm from Baseline and the lesion is subsequently histologically confirmed, then it will count as a nSEB for the purposes of analysis.

Primary Estimand

The primary estimand – “Treatment policy” is defined as follows:

The difference in rates of nSEBs if subjects were to continue to be treated for the entire study unless forced to discontinue treatment due to an AE or lack of efficacy. The imputation of missing data in accordance with this estimand is discussed in detail in [Section 3.2](#).

The treatment policy estimand assesses the expected effect on nSEBs in a patient population offered treatment with Patidegib Topical Gel, 2%, as compared to vehicle.

This endpoint will be analyzed using a Negative Binomial regression to compare treatment groups, with number of BCCs that are not SEBs at Baseline, prior HHI therapy, gender, age █),

Pelle-926-301 Statistical Analysis Plan

17 June 2020

and geographic region strata (North America, Europe), as covariates. PROC GENMOD of SAS will be used with distribution=NEGBIN.

A non-parametric rank analysis of covariance (ANCOVA, Stokes et al) will be provided as a sensitivity analysis with number of BCCs that are not SEBs at Baseline, prior HHI therapy, gender, age (█ years old), and geographic region as covariates.

The Negative Binomial regression was selected as the primary method of analysis to account for the potential for overdispersion. Using the Negative Binomial model, the power will be somewhat higher than the one calculated using a non-parametric Wilcoxon-Mann-Whitney test. The proposed sensitivity analysis, Rank ANCOVA, was selected to corroborate the results from the Negative Binomial model. If the distribution is markedly different from Negative Binomial (and unknown to sufficiently allow a different parametric regression model), then the non-parametric ANCOVA gives type-1 error closer to the nominal level.

Analysis	ITT		PP	
	Negative Binomial	Rank	Negative Binomial	Rank
MI	x; s	x; s		
LOCF	x	x		
OC	x	x	x; s	x; s
Derived	Listing Only			

Note: 'x' denotes that the full population will be used, and 's' denotes that subgroup analyses will be provided in the given population and analysis type.

The primary method for dealing with missing data will be the multiple imputation (MI) method discussed in detail in [Section 3.2](#). An analysis in the PP Population using the observed case (OC) method with the offset option specified to account for different follow-up times will be provided as a sensitivity analysis. A box plot of the mean number of nSEBs per subject over time will be presented. Additionally, a stacked histogram showing the proportion of subjects with 0, 1, 2, 3, 4, and █ nSEBs will be presented over time in the ITT Population.

Last Observation Carried Forward (LOCF) and OC analyses using both the Negative Binomial and Rank ANCOVA models will be done as sensitivity analyses. Additional sensitivity analyses (conservative multiple imputations and tipping point analysis) are described in [Section 3.2](#).

The derived number of nSEBs, determined using the actual measurements provided instead of relying on the answer to the question "Lesion has a longest diameter █ mm and has grown by at least █ mm in longest diameter from Baseline:", will be presented in the listings. If the post-baseline measurement is missing which makes the derivation impossible and the baseline measurement is present, then the question will be used instead to determine if the BCC qualifies as a nSEB. However, if there is no baseline measurement, then the lesion will not count as a nSEB.

Pelle-926-301 Statistical Analysis Plan

17 June 2020

Listings of derived efficacy endpoints, BCC measurements, facial BCC procedures, and digital imaging of BCCs will be created.

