5 STUDY OBJECTIVES

5.1 Primary Objective

The primary objective of the study is to assess the number of new BCCs in the 2 arms (Patidegib Topical Gel, 2%, and Vehicle) when applied twice daily to the face of subjects with Gorlin Syndrome.

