12.6.1.1 Primary Endpoint

The primary endpoint is the number of new BCCs per subject by Month 12.

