12.6.1.2 Secondary Endpoints

The secondary efficacy endpoints are:

1. The number of nSEBs per subject by Month 12.
2. The proportion of subjects developing ≥ 2 facial new BCCs by Month 12.
3. The proportion of subjects developing ≥ 1 facial new BCCs by Month 12.
4. The number of new BCCs per subject by Month 9.
5. The number of new BCCs per subject by Month 6.
6. aBCCdex change in Lesion Symptoms scale score from Baseline to Month 12.

An nSEB is a histologically verified BCC that was surgically removed because of possible functional facial/health impairment as determined by the Investigator.

Also, nSEBs are facial BCCs with a longest diameter of [REDACTED] that:

- a. were not surgically eligible BCCs (SEBs) at Baseline,
- b. have grown by [REDACTED] in longest diameter from Baseline, and
- c. have been verified histologically.

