12.6.2 Efficacy Analyses

The primary endpoint is the number of new BCCs per subject that develop from baseline to Month 12. The number of new BCCs that develop from Baseline to Month 12 will be analyzed using a negative binomial regression to compare treatment groups with number of BCCs at Baseline, Age [REDACTED], gender, prior HHI therapy, and geographic region strata (North America, Europe) as covariates. PROC GENMOD of SAS will be used with distribution=Negbin.

In order to assess the impact of parametric assumptions, a non-parametric rank analysis of covariance (ANCOVA, Stokes et al) will be provided as a sensitivity analysis with number of BCCs at Baseline, prior HHI therapy, gender, age [REDACTED], and geographic region as covariates.

The Negative Binomial regression was selected as the primary method of analysis to account for the potential for overdispersion. Using the Negative Binomial model, the power will be somewhat higher than the one calculated using a non-parametric Wilcoxon-Mann-Whitney test. The proposed sensitivity analysis, Rank ANCOVA, was selected to corroborate the results from the Negative Binomial model. If the distribution is markedly different from Negative Binomial (and unknown to sufficiently allow a different parametric regression model), then the non-parametric ANCOVA gives type-1 error closer to the nominal level.

The number of nSEBs that develop from Baseline to Month 12 will be analyzed using a Negative Binomial regression to compare treatment groups with number of BCCs at Baseline, Age [REDACTED], gender, prior HHI therapy, and geographic region as covariates. Secondary endpoints that are based on number of new BCCs will be analyzed similar to the primary endpoint. The proportion of subjects with at least two new BCCs lesions and the proportion of subjects with at least one new BCC lesion will be analyzed using a logistic regression to compare treatment groups with number of BCCs at Baseline, Age [REDACTED], Gender, and prior HHI therapy and geographic region as covariates. Change in aBCCdex will be analyzed using an ANCOVA model with treatment group as a main effect, Baseline aBCCdex, prior HHI therapy, gender, age strata, and geographic region as covariates. Testing of secondary endpoints will be done sequentially at a two-sided 0.05 level.

The primary method for dealing with missing data will be the MI method discussed in detail in Section 12.7.6.

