LOCF and observed case analyses will be done as sensitivity analyses.

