12.7.6 Handling of Missing Data

The primary method for dealing with missing data will be the MI method. The MI model will be detailed in the SAP. One hundred imputations will be generated using PROC MI of SAS. Fully Conditional Specification (FCS) model will be used with either new BCCs or nSEBs at prior post-Baseline visits, treatment group, number of BCCs at Baseline, prior HHI therapy, gender, age strata, and geographic region as covariates to impute the data. The seed to be used is 20180330. The results of the 100 analyses will be transformed into a normal statistic and combined into a single analysis using PROC MIANALYZE.

LOCF and observed case analyses will be done as sensitivity analyses.

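### The SAP makes nSEBs the primary endpoint and gates new BCCs behind it, although the protocol made new BCCs primary at the FDA's request

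*SAP*

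**What the plan says.** **Protocol.** Section 5.1: "The primary objective of the study is to assess the number of new BCCs in the 2 arms". Section 12.6.1.1: "The primary endpoint is the number of new BCCs per subject by Month 12". Section 12.6.1.2 lists as its first secondary endpoint: "The number of nSEBs per subject by Month 12". Secondaries 2 to 5 (two responder proportions, and counts by Months 9 and 6) are all based on new BCCs. The synopsis and Section 12.8 describe nSEBs as the original primary endpoint and say the FDA requested the change.

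**SAP, 17 June 2020.** Section 2.5.1: "The primary endpoint is the number of nSEBs per subject by Month 12". Sections 1.2 and 1.3.1 agree with it. Section 2.5.2 puts new BCCs first among the secondaries, bases secondaries 2 to 5 on nSEBs, and opens secondary testing only if the primary endpoint is significant.

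**Analysis of new BCCs.** Protocol 12.6.2 gives the primary model: "The number of new BCCs that develop from Baseline to Month 12 will be analyzed using a negative binomial regression to compare treatment groups". It adds a rank-based sensitivity analysis ("In order to assess the impact of parametric assumptions, a non-parametric rank analysis of covariance") and says "LOCF and observed case analyses will be done as sensitivity analyses". For multiple imputation (MI), Protocol 12.7.6 gives an outline and then defers: "The MI model will be detailed in the SAP".

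**The concern.** A trial has one confirmatory verdict, and here it depends on which document is followed. If the endpoints disagree, the documents reach opposite conclusions on whether the trial met its primary endpoint. The SAP's gate makes this worse, because the endpoint the FDA asked for can be formally tested only after another endpoint has succeeded.

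Nor is this a declared departure from the protocol. SAP Section 4 says it overrides the protocol text that it cites. It does not cite the choice of endpoint, and in reporting the change from a Poisson to a negative binomial model it says the primary endpoint is unchanged.

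The mismatch also goes deeper than a label. The SAP's estimand, baseline covariate, lesion-counting rules, imputation variable and tipping-point analysis are all written for nSEBs. Relabelling the endpoint would leave the protocol's primary analysis without the detail that the protocol defers to the SAP.

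**Working it through.** **1. The documents side by side**

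| Item | Protocol | SAP |
|---|---|---|
| Primary endpoint | New BCCs by Month 12 (12.6.1.1) | nSEBs by Month 12 (2.5.1) |
| First secondary | nSEBs (12.6.1.2) | New BCCs (2.5.2) |
| Secondaries 2–5 | New BCCs | nSEBs |
| Gate | Secondaries tested in sequence at 0.05 (12.7.8) | Secondaries tested only if nSEBs are significant (2.5.2) |
| Baseline covariate, primary model | Number of BCCs (12.6.2) | Number of BCCs that are not SEBs (2.5.1) |
| Lesion history in the MI model | New BCCs or nSEBs at earlier post-baseline visits (12.7.6) | Change in number of SEBs; results used to derive nSEBs (3.2) |
| Estimand | None stated | Difference in nSEB rates (2.5.1) |
| Tipping point | None stated | Shift in the increase in nSEBs (3.2) |

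SAP 3.2 applies MI to the count secondaries, which include new BCCs, but names no imputation variable for them. The merged-lesion rule (2.5.1) and the date-first-reported rule (3.2) cover nSEBs only.

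**2. The plan's own power figure, for nSEBs**

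Inputs: 6-month means of 1.4 (vehicle) and 0.6 (patidegib) and vehicle SD 1.52, from SAP 2.2; patidegib SD 0.94, from the protocol synopsis; 63 per arm; two-sided 0.05.

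- Pooled SD = √((1.52² + 0.94²)/2) = 1.264.
- Effect size = (1.4 − 0.6)/1.264 = 0.633, against the stated 0.63. Doubling means and SDs for Month 12 leaves it unchanged.
- Normal-approximation power = Φ(0.633 × √(63/2) − 1.96) = Φ(3.553 − 1.96) = 94.4%. Wilcoxon-Mann-Whitney variants gave 91.0% to 97.7%. The plan's claim of more than 90% holds.
- Randomized = 126/(1 − 0.16) = 150, as stated.

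All of this concerns nSEBs. For new BCCs, Protocol 12.8 says only that power would be the same if the proportional effect matches and the coefficients of variation are similar. It gives no mean or SD for the new primary endpoint.

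**3. How often the two documents would disagree**

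Treat the two test statistics as bivariate normal with correlation ρ, and set each mean so that a two-sided 0.05 test has the stated power. Power p gives mean μ where P(|Z + μ| > 1.96) = p; for example, 90% gives μ = 3.242 and 70% gives 2.484. The disagreement probabilities are P(nSEB significant, new BCC not) and P(new BCC significant, nSEB not). The second is the barred case. New-BCC power and ρ are assumptions.

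| nSEB power | New-BCC power | Outcome | ρ = 0.5 | ρ = 0.7 | ρ = 0.9 |
|---|---|---|---|---|---|
| 90% | 90% | SAP success only | 6.8% | 5.3% | 3.1% |
| | | New BCC barred | 6.8% | 5.3% | 3.1% |
| | | Total | 13.5% | 10.6% | 6.2% |
| 90% | 70% | SAP success only | 23.5% | 21.8% | 20.2% |
| | | New BCC barred | 3.5% | 1.8% | 0.2% |
| 90% | 95% | SAP success only | 3.1% | 2.1% | 0.7% |
| | | New BCC barred | 8.1% | 7.1% | 5.7% |
| 94.4% | 94.4% | Total | 8.3% | 6.6% | 4.0% |

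Check: the two directions must differ by the difference in power. At 90% and 70% with ρ = 0.5, 0.2347 − 0.0347 = 0.20.

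**4. Error rate if the choice stayed open**

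If either endpoint could be called primary after unblinding, each at 0.05, the familywise error would be 1 − 0.95² = 9.75% under independence, and at most 10% by Bonferroni.

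**The case against.** The strongest reply is version lag. The SAP refers to a planned interim analysis, a Section 12.9 on sample size, an Imaging Review Charter and a Poisson model, none of which is in the supplied protocol. The identifier of the protocol it implements is redacted in SAP Section 1. If the FDA's request came after June 2020, Section 4 could not have listed it, and its statement that the endpoint is unchanged was true of the protocol then in force. Protocol Section 12 requires only that the SAP be final before unblinding, so an update could have followed. This is very likely how the conflict arose. It does not resolve the conflict: no aligned SAP is in the documents, and the one supplied cannot be run as the protocol's primary analysis.

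A second reply is that the protocol already covers most of the gap. In part it does. Sections 12.6.2 and 12.7.6 fix the model, rank ANCOVA, LOCF, observed-case analysis, imputation predictors, number of imputations and seed. Sections 6.1.4 and 6.1.5 give new tumors new numbers and exclude baseline lesions from the count. Still missing are a new-BCC estimand, a merged-lesion rule, a date-first-reported rule and a settled imputation variable.

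A third reply is that the disagreement rates rest on assumed inputs and on nSEB power of 90%, where the plan's own figures give 94.4%. That is fair: with both endpoints at 94.4% the rates fall to 8.3%, 6.6% and 4.0%. The contradiction itself depends on none of these figures.

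**Conclusion.** The concern holds, and it must be fixed. The conflict over the primary endpoint is explicit, is not declared in SAP Section 4, and runs through the hierarchy, estimand, covariate, imputation and sensitivity analyses. Confidence in the mismatch is high.

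Its consequence is less certain. At equal power of 90% to 94.4%, the documents would disagree in about 4% to 13.5% of trials over correlations of 0.9 to 0.5. If new-BCC power were only 70%, the SAP would declare success on its own in roughly one trial in five or more. These ranges rest on the bivariate normal model and the assumed new-BCC power and correlations.

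The documents do not show whether this SAP still governs or whether the study is still blinded.

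**What to change.** Before unblinding, either confirm that a later SAP already does the following or reissue this one.

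- **Endpoint and order.** Make new BCCs by Month 12 primary, followed by the secondaries as listed in Protocol 12.6.1.2. State in the SAP that this list is the testing order and that it is gated on new BCCs; the protocol says only that testing is sequential.
- **Primary model.** Move the new-BCC negative binomial model of SAP 2.5.2 to the primary analysis. Its visible covariates match Protocol 12.6.2; the age strata are redacted in both, so check them.
- **Supporting text.** Rewrite SAP 1.2, 1.3.1, 2.5.1, 2.5.2 and 3.2 for new BCCs: estimand, rules for merged lesions and date first reported, an imputation variable with the predictors of Protocol 12.7.6, rank ANCOVA, LOCF and observed case. Carry over the SAP's vehicle-based imputation and tipping-point analyses, which the protocol does not require but the SAP already plans.
- **Sample size.** In SAP 2.2 keep the nSEB calculation, label it as based on the original primary endpoint, and add the protocol's conditional statement on new-BCC power.
- **Record.** Enter the endpoint change in SAP Section 4.

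Separately, the Phase 2 mean of 0.42 is attributed to new BCCs in the protocol synopsis, while SAP Section 4 says it refers to nSEBs. The sponsor should reconcile this against the Phase 2 report.

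The cost is one SAP revision, or confirmation of a later version, with no new data and no effect on patients. If unblinding has already occurred, a revision can no longer count as prespecified.

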2.5.2 Secondary Efficacy Analysis

The secondary efficacy endpoints are:

1. The number of new BCCs that develop from Baseline to Month 12.
2. The proportion of subjects developing ≥ 2 facial nSEB(s) by Month 12.
3. The proportion of subjects developing ≥ 1 facial nSEB(s) by Month 12.
4. The number of qualifying nSEBs per subject at Month 9 (defined as the number of qualifying nSEBs per subject by Month 9).
5. The number of qualifying nSEBs per subject at Month 6 (defined as the number of qualifying nSEBs per subject by Month 6).
6. Advanced BCC Index (aBCCdex) change in lesion score from Baseline to Month 12.

The number of new BCCs that develop from Baseline to Month 12 will be analyzed using a negative binomial regression to compare treatment groups with number of BCCs at Baseline, Age (█████ years), gender, prior HHI therapy, and geographic region strata (North America, Europe) as covariates. Secondary endpoints that are based on number of nSEBs will be analyzed similar to the primary endpoint. The proportion of subjects with at least 2 nSEB lesions and the proportion of subjects with at least 1 nSEB lesion will be analyzed using a logistic regression to compare treatment groups with number of BCCs that are not SEBs at Baseline, Age (█████ years), gender, prior HHI therapy, and geographic region strata (North America, Europe) as covariates. Change in aBCCdex scores will be analyzed using an ANCOVA model with treatment group as a main effect, the corresponding baseline aBCCdex scale score, prior HHI therapy, gender, age █████ old), and geographic region strata as covariates. Please see Appendix A for the scoring instructions for the aBCCdex lesion scale score. A box plot of the number of new BCCS per subject over time will be presented. An analysis of the number of new BCCs by Month 12 in the PP Population using OC will be provided as a sensitivity analysis.

The secondary endpoints will be tested sequentially in the order above using a gatekeeping strategy with type-1 error of 0.05 at 12 months. If and only if the primary endpoint is statistically significant will the secondary efficacy endpoints be tested using the gate-keeping procedure.

All efficacy assessments (secondary and exploratory endpoints) will be summarized descriptively by treatment group and visit.

